1.2 Secondary Objectives

- 1.2.1 To observe and record anti-tumor activity. Although the clinical benefit of pinometostat has not been fully established, the intent of offering this treatment is to provide a possible therapeutic benefit, and thus the patient will be carefully monitored for tumor response and symptom relief in addition to safety and tolerability
- 1.2.2 Estimate biologic activity of 7 day window treatment of pinometostat monotherapy
- 1.2.3 Estimate the toxicity profile of pinometostat alone (week 1) and in combination with daunorubicin and cytarabine
- 1.2.4 Estimate event free and overall survival of patients with MLL rearranged acute myeloid leukemia after combination treatment with pinometostat, daunorubicin, and cytarabine
- 1.2.5 Estimate the early death rate (death \leq 30 days) of pinometostat, daunorubicin, and cytarabine
- 1.2.6 Determine the rate of MRD negativity by clinical flow cytometry on post-treatment recovery bone marrow

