2. BACKGROUND

2.1 Acute Myeloid Leukemia

Acute myeloid leukemia (AML) is a cancer of developing hematopoietic progenitors in which a differentiation block causes the accumulation of nonfunctional precursor cells with the functional consequence of rapid progression to severe and ultimately fatal complications such as dysfunctional immunity, myelophthisic and/or immune cytopenias (with attendant consequences), or hyperviscosity. The standard therapy for younger, fit patients includes intensive induction chemotherapy over the course of a week with combination of an anthracycline (typically daunorubicin) and nucleoside analogue (cytarabine; the combination being called “7+3”), a prolonged hospitalization and peripheral blood count recovery, and for all but very good risk patients, consolidation with an allogenic stem cell transplant, if a donor is

available. About 60-80% of younger patients can achieve a complete remission, but despite this only about a third are ultimately cured.¹ Older patients or those who are not fit for high intensity induction chemotherapy may be treated with hypomethylating agents (azacitidine and decitabine) with varying levels of remission induction rates and improvement in progression free survival, but not cure.²

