Length of study treatments

Study treatment will end after either 35 days (first induction) or 28 days (with calendar reset to day 1 on the first day of 5+2 in second induction attempt) of pinometostat. Patients should then receive standard of care consolidative therapy including allogeneic bone marrow transplant, but these are not considered study treatments. No specific consolidation is mandated.

Follow-up period

Patients will be followed until the soonest of death, alternative leukemia therapy (i.e. for relapsed or refractory disease; this is excluding the planned consolidation that may directly follow the study treatment) initiated, enrollment on another therapeutic clinical trial, bone marrow transplantation, voluntary or involuntary withdrawal from study (see section 6.5) or lost to follow-up.

Toxicity assessment

All patients who receive any amount of the study drug will be evaluable for toxicity. Toxicity will be graded and reported according to the Common Terminology Criteria for Adverse Events (CTCAE) Version 5. The CTEP Active Version of the CTCAE is identified and located on the CTEP website at http://ctep.cancer.gov/protocolDevelopment/electronic_applications/ctc.htm. All appropriate treatment areas should have access to a copy of the CTEP Active Version of CTCAE.

It is recognized that drug-related toxicity in this population may be difficult to ascertain, given the aggressive hematologic disease. Investigators will attempt to assign attribution of toxicities to each drug if possible. Toxicity attributed to any of the three agents will be considered dose limiting. Dose limiting toxicity will be divided into non-hematologic and hematologic toxicity.

Dose-limiting toxicity

Definitions of dose-limiting toxicities are in section 6.2.

Patients who receive at least 1 dose of pinometostat during cycle 1 will be considered to be evaluable for toxicity/DLT and will not be replaced during the dose escalation phase of the trial unless the PI determines that further additional patients at that dose level are required for safety purposes; the context in which DLTs are noted (before or after the introduction of 7+3) will be considered in this decision. Patients with transient liver function test abnormalities (AST, ALT, bilirubin, or alkaline phosphatase) that resolve to < grade 1 within 5 days will not be considered DLT. Infection will not constitute DLT unless it is felt that the infection resulted from

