9.3 Analysis of Secondary Endpoints

Secondary endpoints we are evaluating are:

- Toxicity frequencies for each patient, according to CTCAE v5
- Time to hematologic count recovery will be analyzed using lab evaluation of complete blood counts and differential
- Differential blast counts between screening and day 8 will be analyzed using lab evaluation of complete blood counts and differential
- Rate of MRD positivity will be evaluated by multiparameter flow cytometry, next-generation sequencing (or both) after induction therapy among those patients who attain morphologic and cytogenetic CR
- Progression free survival for all patients, defined as the time from the start of study treatment until progression or death, whichever occurs earliest. Patients will be censored at earliest of loss to follow-up, allogeneic stem-cell transplantation, or initiation of other anti-leukemia therapy when in remission
- Overall survival for all patients

Every report will contain all patients included in the study. For the response calculation, the report will contain at least a section with all eligible patients. Another section of the report may detail the response rate for evaluable patients only. The maximum grade for each type of toxicity will be recorded for each patient, and frequency tables will be reviewed to determine toxicity patterns. CR rate and Rate of MRD positivity will be calculated with the exact binomial 95% confidence intervals. The Kaplan-Meier method will be used to estimate time to progression and overall survival.

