9.4 Phase 2 portion: Reporting and Exclusions

9.4.1 Evaluation of Toxicity

All patients will be evaluable for toxicity from the time of their first treatment with pinometostat.

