10.1.1 CAEPRs for CTEP IND Agent(s)

10.1.1.1 CAEPR for pinometostat

Comprehensive Adverse Events and Potential Risks list (CAEPR) for Pinometostat (EPZ-5676, NSC 795144)

The Comprehensive Adverse Events and Potential Risks list (CAEPR) provides a single list of reported and/or potential adverse events (AE) associated with an agent using a uniform presentation of events by body system. In addition to the comprehensive list, a subset, the Specific Protocol Exceptions to Expedited Reporting (SPEER), appears in a separate column and is identified with bold and italicized text. This subset of AEs (SPEER) is a list of events that are protocol specific exceptions to expedited reporting to NCI (except as noted below). Refer to the 'CTEP, NCI Guidelines: Adverse Event Reporting Requirements' http://ctep.cancer.gov/protocolDevelopment/electronic_applications/docs/aeguidelines.pdf for further clarification. The CAEPR does not provide frequency data; refer to the Investigator's Brochure for this information. Below is the CAEPR for Pinometostat (EPZ-5676).

NOTE: Report AEs on the SPEER **ONLY IF** they exceed the grade noted in parentheses next to the AE in the SPEER. If this CAEPR is part of a combination protocol using multiple investigational agents and has an AE listed on different SPEERs, use the lower of the grades to determine if expedited reporting is required.

| Adverse Events with Possible Relationship to Pinometostat (EPZ-5676) (CTCAE 5.0 Term) | Specific Protocol Exceptions to Expedited Reporting (SPEER) |
|--|---|
| BLOOD AND LYMPHATIC SYSTEM DISORDERS | |
| Anemia | |
| Febrile neutropenia | Febrile neutropenia (Gr 2) |
| Leukocytosis | |
| CARDIAC DISORDERS | |
| Heart failure | |
| GASTROINTESTINAL DISORDERS | |
| Diarrhea | |
| Nausea | |
| Vomiting | |
| GENERAL DISORDERS AND ADMINISTRATION SITE CONDITIONS | |
| Fatigue | |
| INVESTIGATIONS | |
| Alanine aminotransferase increased | |
| Aspartate aminotransferase increased | |
| Blood bilirubin increased | |
| Electrocardiogram QT corrected interval prolonged | |
| Lymphocyte count decreased | |
| Neutrophil count decreased | |
| Platelet count decreased | |
| White blood cell decreased | |
| METABOLISM AND NUTRITION DISORDERS | |
| Hypocalcemia | |
| Hypophosphatemia | |
| SKIN AND SUBCUTANEOUS TISSUE DISORDERS | |
| Rash maculo-papular | |

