11. STUDY CALENDAR

Baseline evaluations are to be conducted within 1 week prior to start of protocol therapy. In the event that the patient's condition is deteriorating, laboratory evaluations should be repeated in order to decide if therapy should be continued.

Table 11.1: Initial treatment plan.

| | Pre-Study / Screening | Wk 1 | Wk 2 | Wk 3 | Wk 4 | Wk 5 | Off Study ^c | Long Term Follow-Up ^f |
|---|-----------------------|------|----------------|------|------|----------------|------------------------|----------------------------------|
| Pinometostat | | A | A | A | A | A | | |
| Cytarabine | | | B | | | | | |
| Daunorubicin | | | C | | | | | |
| Informed consent | X | | | | | | | |
| Demographics | X | | | | | | | |
| Medical history | X | | | | | | | |
| Concurrent meds | X | X | X | X | X | X | | |
| Physical exam | X | X | X | X | X | X | X | |
| Vital signs | X | X | X | X | X | X | X | |
| Height and Weight | X | X | X | X | X | X | X | |
| Performance status | X | | | | | | | |
| CBC w/diff, plts, PT/INR, aPTT | X | X | X | X | X | X | X | |
| Serum chemistry ^a | X | X | X | X | X | X | X | |
| EKG (as indicated) | X | | | | | | | |
| Echocardiogram/MUGA | X | | | | | | | |
| Adverse event evaluation | | X | X | X | X | X | | |
| B-HCG | X ^b | | | | | | | |
| Bone marrow aspiration and biopsy | X | | X | | X | X ^d | | |
| Bone marrow metaphase karyotype | X | | X | | X | X ^d | | |
| Bone marrow MLL (KMT2A) translocation by FISH | X | | X | | X | X ^d | | |
| Immunophenotyping (BM and PB) | X | | X | | | X ^d | | |
| Differentiation analysis | X | | X ^e | | | X ^d | | |
| Comprehensive mutational profile | X | | X ^e | | | X ^d | X | |
| Survival | | | | | | | | X ^f |

A: Pinometostat: Dose as assigned; weeks 1-5, days 1-35
B: Cytarabine: 100 mg/m² continuous IV infusion; week 2, days 8-14
C: Daunorubicin: 60 mg/m² IV; daily days 8-10 of week 2
a Albumin, alkaline phosphatase, total bilirubin, bicarbonate, BUN, calcium, chloride, creatinine, glucose, uric acid, LDH, phosphorus, potassium, total protein, SGOT [AST], SGPT [ALT], sodium.
b. Serum or urine pregnancy test (women of childbearing potential).
c. Off-study evaluation.
d. And at count recovery in week 5 or beyond
e. Day 8 of week 2, and at relapse (if applicable)

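### The worst-grade toxicity table in section 9.3 has no pre-dose reference and no week-1 split, so it cannot deliver the single-agent profile in objective 1.2.3

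*Combined protocol and SAP*

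**What the plan says.** Objective 1.2.3 is to "Estimate the toxicity profile of pinometostat alone (week 1) and in combination with daunorubicin and cytarabine". Section 9.3 lists the matching endpoint as "Toxicity frequencies for each patient, according to CTCAE v5" and gives the summary rule: "The maximum grade for each type of toxicity will be recorded for each patient, and frequency tables will be reviewed to determine toxicity patterns".

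The counting window opens at first dose. Section 9.4.1, under the Phase 2 reporting heading, says "All patients will be evaluable for toxicity from the time of their first treatment with pinometostat". The toxicity paragraph of section 9.1 likewise makes anyone who receives any study drug evaluable.

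On causation, section 9.1 concedes that the aggressive disease makes drug toxicity hard to identify, and adds that "Investigators will attempt to assign attribution of toxicities to each drug if possible". Section 10.2 supplies a five-level attribution scale, from definite to unrelated, defined against the study treatment. Section 9.3 does not mention attribution.

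In Table 11.1 the row "Adverse event evaluation" starts in week 1 and is blank at screening. CBC with differential, serum chemistry, medical history, physical examination and performance status are all marked at screening.

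**The concern.** A maximum grade with no reference point answers how bad a value was at its worst. It does not say whether the value began or worsened on treatment. The gap matters in this trial for four reasons.

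- Section 2.1 names cytopenias among the consequences of AML itself. Section 3.1.3 admits only previously untreated patients (hydroxyurea and, in one case, ATRA excepted), and section 3.1.6 sets no neutrophil, platelet or hemoglobin minimum.
- Five events on the pinometostat CAEPR (section 10.1.1.1) are abnormalities that the disease also produces: anemia and decreases in lymphocytes, neutrophils, platelets and white cells. "Neutrophil count decreased" is one of them. Leukocytosis is listed too. Section 2.2.3 reads it as a possible sign of differentiation, yet patients needing hydroxyurea for high counts are eligible.
- There is no control arm, so each patient's own pre-dose grade is the natural comparator.
- 7+3 starts on day 8. A single maximum over the whole course mixes the pinometostat-alone week with induction chemotherapy, for which section 10.1.2 expects cytopenias and anemia.

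At stake is what the descriptive toxicity endpoint can conclude about pinometostat alone. No decision rule in the trial depends on it.

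**Working it through.** The plan states no figure for this point, so there is none to reproduce. The check has a reading part and an illustration.

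**Is a baseline rule given anywhere?** Sections 6.2, 7, 9.1, 9.3, 9.4, 10 and 11 were read for one. No section defines a treatment-emergent event for analysis or compares an on-treatment grade with the screening grade. The term is applied to adverse events once, in section 7, about chemotherapy dose modification. No section states a toxicity table for week 1 alone or a table by attribution.

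**Can a baseline be formed from planned data?** For laboratory events, yes: CBC and chemistry are scheduled at screening, and section 11 puts baseline evaluations within one week before therapy. For symptoms, only partly: history and examination are recorded, but no graded symptom assessment is specified before dosing.

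**How large could the effect be in week 1?** Let *b* be the share of patients already at grade 3 or above for a cytopenia before dosing, and *w* the share of the others who newly reach it in days 1-7. Both are assumptions. The illustration also assumes that a pre-existing grade is still present after first dose and is recorded as an event.

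- Worst-grade table: *b* + (1 − *b*)*w*
- New events among all patients: (1 − *b*)*w*
- Share of tabulated cases present before dosing: *b* / [*b* + (1 − *b*)*w*]

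| *b* | *w* | Worst-grade table | New events, all patients | Present before dosing |
|---|---|---|---|---|
| 20% | 5% | 0.20 + 0.80×0.05 = 24% | 4% | 0.20/0.24 = 83% |
| 20% | 20% | 0.20 + 0.80×0.20 = 36% | 16% | 0.20/0.36 = 56% |
| 40% | 5% | 0.40 + 0.60×0.05 = 43% | 3% | 0.40/0.43 = 93% |
| 40% | 20% | 0.40 + 0.60×0.20 = 52% | 12% | 0.40/0.52 = 77% |
| 60% | 5% | 0.60 + 0.40×0.05 = 62% | 2% | 0.60/0.62 = 97% |
| 60% | 20% | 0.60 + 0.40×0.20 = 68% | 8% | 0.60/0.68 = 88% |

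Section 9.2 gives a sample size of 6 to 37. With *b* = 40% and *w* = 5%, the maximum of 37 gives 37 × 0.43 = 15.9 patients tabulated and 37 × 0.03 = 1.1 with a new event. The minimum of 6 gives 6 × 0.43 = 2.6 and 6 × 0.03 = 0.2.

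These figures describe a week-1 table only. Over the whole course, cytopenias from 7+3 would enter both columns.

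**The case against.** The strongest reply is that the plan already knows about disease confounding and deals with it elsewhere. Section 9.1 acknowledges it, attribution is collected, and the scale includes unrelated. Section 6.2 requires relatedness for a non-hematologic DLT and allows failed count recovery with persistent disease to be discounted. Section 7 excludes hematologic toxicities from pinometostat dose reduction. Several non-hematologic baselines are bounded at entry: liver tests, creatinine and coagulation (3.1.6), LVEF (3.1.8), and 72 hours afebrile for patients on antimicrobials (3.2.11).

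Much of this stands. It shows that the problem is mitigated, lies mainly with cytopenias, and does not reach dosing decisions or the remission test. It does not close the gap. Attribution is attempted only where possible, and section 9.3 does not say that it enters the table. The DLT rules apply to Phase 1b alone and do not define the secondary toxicity table.

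Two stronger readings are tempting, and the documents do not support them. A reader might infer that disease cytopenias will be reported as pinometostat toxicity. Section 9.3 puts no such label on the table. A reader might also infer from the blank screening cell that every pre-existing condition is first graded on drug. Screening laboratory values can be graded, and the blank cell does not show how pre-existing findings will be entered. The case report forms that would settle this are not in the documents.

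A further fair objection is that comparing the pre-dose grade with an overall maximum would still absorb 7+3 cytopenias. That is correct, and it is why the split by period is needed as well as the baseline comparison.

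**Conclusion.** The point holds as a gap in a descriptive secondary analysis. Followed as written, section 9.3 can count abnormalities present at entry, and it cannot isolate the week-1 profile in objective 1.2.3.

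The direction is clear for any event common before dosing. The size is not known. The contrast of 24-68% tabulated against 2-16% new rests on assumed rates (20-60% pre-dose, 5-20% newly affected) that the documents neither give nor contradict. It should not be carried over to the whole-course table, where chemotherapy contributes from day 8.

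A baseline comparison will not make the week-1 estimate precise, because new events may be few. Nor will it separate drug effect from leukemia that worsens during week 1, or from hydroxyurea given alongside. Attribution remains useful for that. Sample size, error rates, DLT rules and the primary efficacy test are unaffected.

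**What to change.** Amend section 9.3 as follows.

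- Tabulate events that are new, or worse in grade than the last pre-dose grade, separately for days 1-7 (pinometostat alone) and for the combination period. Section 6.1.8 allows 7+3 to begin early, so split at each patient's actual 7+3 start date.
- For laboratory toxicities, give a shift table of screening grade against maximum grade in each period, using the CBC and chemistry already scheduled.
- Show results by the attribution already collected.
- Mark baseline symptom grading at the existing screening visit in Table 11.1.
- Keep the all-cause maximum-grade table as a supplement.

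The cost is SAP wording, programming, a longer toxicity table and one baseline grading entry per patient. No visit or sample is added. Section 13.1 already requires an amendment before Phase 2 enrollment, which is a natural place for the table definitions. The screening symptom entry should be in place before patients enroll, because ungraded baseline symptoms are hard to reconstruct afterwards.

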9.4 Phase 2 portion: Reporting and Exclusions

9.4.1 Evaluation of Toxicity

All patients will be evaluable for toxicity from the time of their first treatment with pinometostat.

9.4.2 Evaluation of Response

All patients included in the study must be assessed for response to treatment, even if there are major protocol treatment deviations or if they are later deemed ineligible. Each patient will be assigned one of the following categories: 1) complete response, 2) partial response, 3) stable disease, 4) progressive disease, 5) early death from malignant disease, 6) early death from toxicity, 7) early death because of other cause, or 9) unknown (not assessable, insufficient data). [Note: By arbitrary convention, category 9 usually designates the “unknown” status of any type of data in a clinical database.]

All of the patients who met the eligibility criteria (with the possible exception of those who received no study medication) should be included in the main analysis of the response rate. Patients in response categories 4-9 should be considered to have a treatment failure (disease progression). Thus, an incorrect treatment schedule or drug administration does not result in exclusion from the analysis of the response rate. Precise definitions for categories 4-9 will be protocol specific.

All conclusions should be based on all eligible patients. Subanalyses may then be performed on the basis of a subset of patients, excluding those for whom major protocol deviations have been identified (*e.g.*, early death due to other reasons, early discontinuation of treatment, major protocol violations, etc.). However, these subanalyses may not serve as the basis for drawing conclusions concerning treatment efficacy, and the reasons for excluding patients from the analysis should be clearly reported. The 95% confidence intervals should also be provided.

Analysis of all correlative studies during this trial will be exploratory. Descriptive statistics (means, medians, standard deviations, interquartile ranges) and graphical explorations will be used to characterize central tendency and variability over time. Values will be log transformed as appropriate to reflect biologic plausibility.

10. ADVERSE EVENTS: LIST AND REPORTING REQUIREMENTS

Adverse event (AE) monitoring and reporting is a routine part of every clinical trial. The

following list of AEs (Section 10.1) and the characteristics of an observed AE (Sections 10.2 and 10.3) will determine whether the event requires expedited reporting via the CTEP Adverse Event Reporting System (CTEP-AERS) **in addition** to routine reporting.

10.1 Comprehensive Adverse Events and Potential Risks List(s) (CAEPRs)

The Comprehensive Adverse Events and Potential Risks list (CAEPR) provides a single list of reported and/or potential adverse events (AE) associated with an agent using a uniform presentation of events by body system. In addition to the comprehensive list, a subset, the Specific Protocol Exceptions to Expedited Reporting (SPEER), appears in a separate column and is identified with bold and italicized text. This subset of AEs (SPEER) is a list of events that are protocol specific exceptions to expedited reporting to NCI (except as noted below). Refer to the 'CTEP, NCI Guidelines: Adverse Event Reporting Requirements' http://ctep.cancer.gov/protocolDevelopment/electronic_applications/docs/aeguidelines.pdf for further clarification.

NOTE: Report AEs on the SPEER **ONLY IF** they exceed the grade noted in parentheses next to the AE in the SPEER. If this CAEPR is part of a combination protocol using multiple investigational agents and has an AE listed on different SPEERs, use the lower of the grades to determine if expedited reporting is required.

10.1.1 CAEPRs for CTEP IND Agent(s)

10.1.1.1 CAEPR for pinometostat

Comprehensive Adverse Events and Potential Risks list (CAEPR) for Pinometostat (EPZ-5676, NSC 795144)

The Comprehensive Adverse Events and Potential Risks list (CAEPR) provides a single list of reported and/or potential adverse events (AE) associated with an agent using a uniform presentation of events by body system. In addition to the comprehensive list, a subset, the Specific Protocol Exceptions to Expedited Reporting (SPEER), appears in a separate column and is identified with bold and italicized text. This subset of AEs (SPEER) is a list of events that are protocol specific exceptions to expedited reporting to NCI (except as noted below). Refer to the 'CTEP, NCI Guidelines: Adverse Event Reporting Requirements' http://ctep.cancer.gov/protocolDevelopment/electronic_applications/docs/aeguidelines.pdf for further clarification. The CAEPR does not provide frequency data; refer to the Investigator's Brochure for this information. Below is the CAEPR for Pinometostat (EPZ-5676).

NOTE: Report AEs on the SPEER **ONLY IF** they exceed the grade noted in parentheses next to the AE in the SPEER. If this CAEPR is part of a combination protocol using multiple investigational agents and has an AE listed on different SPEERs, use the lower of the grades to determine if expedited reporting is required.

| Adverse Events with Possible Relationship to Pinometostat (EPZ-5676) (CTCAE 5.0 Term) | Specific Protocol Exceptions to Expedited Reporting (SPEER) |
|--|---|
| BLOOD AND LYMPHATIC SYSTEM DISORDERS | |
| Anemia | |
| Febrile neutropenia | Febrile neutropenia (Gr 2) |
| Leukocytosis | |
| CARDIAC DISORDERS | |
| Heart failure | |
| GASTROINTESTINAL DISORDERS | |
| Diarrhea | |
| Nausea | |
| Vomiting | |
| GENERAL DISORDERS AND ADMINISTRATION SITE CONDITIONS | |
| Fatigue | |
| INVESTIGATIONS | |
| Alanine aminotransferase increased | |
| Aspartate aminotransferase increased | |
| Blood bilirubin increased | |
| Electrocardiogram QT corrected interval prolonged | |
| Lymphocyte count decreased | |
| Neutrophil count decreased | |
| Platelet count decreased | |
| White blood cell decreased | |
| METABOLISM AND NUTRITION DISORDERS | |
| Hypocalcemia | |
| Hypophosphatemia | |
| SKIN AND SUBCUTANEOUS TISSUE DISORDERS | |
| Rash maculo-papular | |

¹This table will be updated as the toxicity profile of the agent is revised. Updates will be distributed to all Principal Investigators at the time of revision. The current version can be obtained by contacting [contact]. Your name, the name of the investigator, the protocol and the agent should be included in the e-mail.

Adverse events reported on pinometostat (EPZ-5676) trials, but for which there is insufficient evidence to suggest that there was a reasonable possibility that pinometostat (EPZ-5676) caused the adverse event:

CARDIAC DISORDERS - Cardiac arrest

EYE DISORDERS - Periorbital edema

GASTROINTESTINAL DISORDERS - Colitis; Constipation; Mucositis oral

GENERAL DISORDERS AND ADMINISTRATION SITE CONDITIONS - Edema face; Generalized edema; Localized edema; Malaise; Multi-organ failure

INFECTIONS AND INFESTATIONS - Device related infection; Folliculitis; Fungemia; Lung infection; Sepsis; Thrush

INVESTIGATIONS - Alkaline phosphatase increased; Creatinine increased; Ejection fraction decreased; INR increased; Investigations - Other (ECG PR prolongation); Investigations - Other (ejection fraction increased); Investigations - Other (increase in polymorphonuclear neutrophils and/or monocytes)

METABOLISM AND NUTRITION DISORDERS - Anorexia; Hyperkalemia; Hypermagnesemia; Hyponatremia; Hyperuricemia; Hypoalbuminemia; Hypokalemia; Hypomagnesemia; Tumor lysis syndrome

MUSCULOSKELETAL AND CONNECTIVE TISSUE DISORDERS - Pain in extremity

NERVOUS SYSTEM DISORDERS - Dysgeusia; Headache; Intracranial hemorrhage; Ischemia cerebrovascular; Lethargy; Presyncope; Tremor

PSYCHIATRIC DISORDERS - Irritability

RENAL AND URINARY DISORDERS - Acute kidney injury

RESPIRATORY, THORACIC AND MEDIASTINAL DISORDERS - Apnea; Cough; Hypoxia; Pleural effusion; Respiratory failure; Respiratory, thoracic and mediastinal disorders - Other (tachypnea); Sore throat

SKIN AND SUBCUTANEOUS TISSUE DISORDERS - Alopecia; Dry skin; Pruritus

VASCULAR DISORDERS - Hematoma; Hypertension

Note: Pinometostat (EPZ-5676) in combination with other agents could cause an exacerbation of any adverse event currently known to be caused by the other agent, or the combination may result in events never previously associated with either agent.

